4.2 Laboratory data

SAP section 8.3 incorrectly stated SI Unit for Uric Acid as mg/dL. The correct SI is $\mu\text{mol}/\text{L}$ and will be used.

Lab abnormalities:

For analysis of abnormalities across multiple visits such as shift Tables, the worst value will be considered. Lab data will be tabulated using categories below:

1. missing data
2. clinically significant low abnormality
3. non-clinically significant low abnormality
4. normal values
5. non-clinically significant high abnormalities
6. high clinically significant abnormalities

4.3 Vital Signs

- Summary of Vital Sign Abnormalities will be presented for weight as per below criteria for LOW and HIGH. If percent change from baseline is a decrease of 10% or more then the result will be considered as LOW abnormality; whereas if percent change from baseline is an increase of 10% or more the result will be considered as a HIGH abnormality; If percent change from baseline is between 10% decrease or 10% increase the results will be considered as NORMAL.

5. EFFICACY ANALYSES

Efficacy data from T25FW and 9HPT is available from the CLIMB registry for matched progressive MS patients. In addition MRI data was also collected from matched patients in the CLIMB registry data. Analysis from the BCT-101 study will compare results with the CLIMB registry data. Since data for patients in the CLIMB registry was collected at only two timepoints 1 to 2 years apart, each patient's outcome data will be adjusted by assuming linear change between the two timepoints to estimate the change at 28 weeks (i.e. by determining the slope or change in outcome per week using the two timepoints and then using baseline value + 28 weeks

times this slope to determine the estimated value at 28 weeks). Since the change may not be linear other functions may also be explored.

5.19-Hole Peg Test (9-HPT)

Dominant and non-dominant hand will be analyzed separately in addition to together as mentioned in SAP section 9.2.

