6.4. Data Presentation Conventions

Continuous variables (e.g. age) are summarized using descriptive statistics (the number of subjects with available data, the mean, standard deviation (SD), first quartile (Q1), median, third quartile (Q3), minimum and maximum).

Categorical variables (e.g. race) are summarized using counts and percentages. Percentages are calculated using the total subjects within the dose group (or dose group and relevant subgroup when appropriate) being presented.

The following conventions are applied to all data presentations and summaries.

- For continuous variables, all mean, first quartile (Q1), median and third quartile (Q3) values are formatted to one more decimal place than the measured value. Minimum and maximum values are presented with the same number of decimal places as the measured value. For measure of variation, e.g. SD, use two more decimal places than the measured value, unless numbers are in at least 100s and there are space constraints in which case 1 decimal place is fine.
- For categorical variables, the number and percentage of responses are presented in the form XX (XX.X%) where the percentage is in the parentheses.
- Date variables are formatted as DDMMYY for presentation. Time is formatted in military time as HH:MM for presentation.
- Wherever possible, data will be decimal aligned or left aligned or as appropriate to best display the data and column headers. Parenthesis will also be aligned appropriately for best display.
- Hypothesis testing to determine if changes from baseline were statistically significant and comparing these against matched historical controls will be performed and presented in select Tables either as post-text Tables or in the CSR depending upon availability of historical data. Similar additional analyses on the percentage of responders from the current study against matched historical controls may be included in the CSR. Subjects from a historical database will be selected by matching key screening or baseline characteristics.
- P-values, if applicable, will be presented to 3 decimal places. If the p-value is less than 0.001 then it will be presented as <0.001. If the rounded result is a value of 1.000, it will be displayed as >0.999.

The table and listing shells and table of contents provide the expected layout and titles of the tables, listings and figures.

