6.7.3. Change from Baseline

Change from baseline is calculated as (post-baseline result – baseline result).

Percent change from baseline is calculated as (change from baseline/baseline result)*100 as long as baseline is non-zero. If baseline is 0, change from baseline is defined as missing.

If either the baseline or the post-baseline result is missing, the change from baseline and/or percentage change from baseline is set to missing as well.

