9. EFFICACY

9.1. General Considerations

Descriptive statistics for continuous and categorical variables will be presented as described in [Section 6.4](#).

Inferential statistical tests will be performed at Type I error $\alpha = 0.05$ (Two-sided). Since this is a single arm, open label study, hypothesis testing will be performed against a historical database by selection of subjects matched on key screening or baseline characteristics.

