9.2. Analysis of Primary Efficacy Endpoint

The primary objective and endpoints in the study are assessments of safety. The secondary objective and endpoints are assessments of efficacy.

The first secondary endpoint is considered the primary efficacy endpoint for this study.

Efficacy analyses will be performed using the modified mITT and EE populations. If mITT and EE populations are the same then, all efficacy analysis will be performed using mITT population only.

The primary efficacy endpoint will be a responder analysis to see if subjects improve in walking speed as measured by time to complete T25FW (ft/sec.) or improve in finger (fine manual) dexterity as measured by time to complete the 9-HPT (sec.)

A subject will be defined as a responder to study drug if their T25FW walking speed or 9-HPT improves by 25% or more between baseline and Week 28. An improvement of 25% is considered clinically meaningful for MS patients^{4,6}.

All deaths related to disease progression or treatment will be defined as non-responders.

The T25FW, 9-HPT, LCLA and SDMT are part of the current Multiple Sclerosis Functional Composite (MSFC) and described in Additional detail in [the BCT-101-US Protocol, Sections 15.2.1, 15.2.2, 15.2.3, 15.2.6, and 15.2.7](#) in Appendix 1.

The T25FW is a quantitative mobility and leg function performance test based on a timed 25 foot-walk. It is the first component of the MSFC to be administered at each visit. The subject is directed to one end of a clearly marked 25-foot course and is instructed to walk 25 feet as quickly as possible, but safely. The time is calculated from the initiation of the instruction to start and ends when the subject has reached the 25-foot mark. The task is immediately administered again by having the subject walk back the same distance. T25FW score is the average in seconds of the two successive trials. Subjects may use assistive devices when doing this task. An increase in speed for T25FW is considered an improvement.

The MSFC uses a z-score transformation which will be used in assessing the changes in the MSFC.

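### Applying the 25% responder cut-off to CLIMB values interpolated to 28 weeks would shrink each control's change to 0.27–0.54 of its size and, where visit noise is material, understate the control responder rate

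*SAP*

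**What the plan says.** Appendix I, section 5, states that BCT-101 results will be compared with matched CLIMB patients on T25FW and 9-HPT. CLIMB has two timepoints, 1 to 2 years apart, so for every control "outcome data will be adjusted by assuming linear change between the two timepoints to estimate the change at 28 weeks". The estimated 28-week value is baseline plus 28 times the weekly slope. The appendix adds: "Since the change may not be linear other functions may also be explored". It does not mention responders.

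Trial patients are handled differently. Section 9.2 states: "A subject will be defined as a responder to study drug if their T25FW walking speed or 9-HPT improves by 25% or more", with Week 28 set against baseline. Section 6.7.3 states: "Percent change from baseline is calculated as (change from baseline/baseline result)*100 as long as baseline is non-zero". Nothing is rescaled.

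Two passages connect the responder endpoint with the registry. Section 9.1 says that "hypothesis testing will be performed against a historical database by selection of subjects matched on key screening or baseline characteristics". Section 6.4 says: "Similar additional analyses on the percentage of responders from the current study against matched historical controls may be included in the CSR". No passage limits interpolation to mean change, and none defines a CLIMB responder.

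On scale, section 3.2.2 lists T25FW change in ft/sec. Section 9.2 speaks of walking speed in ft/sec but also says "T25FW score is the average in seconds of the two successive trials". The scale on which CLIMB walks are interpolated is not stated.

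**The concern.** A control's observed change has two parts: true change, which accrues with time, and visit-to-visit measurement error, which does not. Scaling by 28/T is right for the first part if change is linear. It also shrinks the second part, and only in the controls. A mean comparison is largely untouched, because noise averages out. A cut-off applied to individuals is not, because noise alone carries some patients past 25%.

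The ≥25% rate on either test is the primary efficacy endpoint. If it were contrasted with interpolated CLIMB values, noise could produce responders in the trial and almost none in the registry, and the difference would look like benefit. The study has no concurrent control and is meant to inform the design of a randomized trial (SAP section 4.3), so such a contrast could mislead that design.

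**Working it through.** The documents give no control responder rate, so there is no plan figure to reproduce.

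**From the documents alone.** Estimated change = (28/T) × observed change, with T the weeks between CLIMB visits. The factor is 28/52 = 0.54 at one year and 28/104 = 0.27 at two. The observed improvement needed to reach an estimated 25% is 0.25 × T/28:

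- T = 52: 46.4%
- T = 78: 69.6%
- T = 104: 92.9%

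For 9-HPT this is a fall in time; for the walk it is a gain in speed. If walk time is interpolated instead, a 25% speed gain is a 20% fall in time, and 0.20 × T/28 gives falls of 37.1%, 55.7% and 74.3%. A trial patient needs 25% on either test.

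**Size, under assumptions.** Visit noise, slopes, registry size and the test are not in the documents. Assumed: lognormal independent visit errors (per visit, after averaging trials), independent slopes for the two tests, T uniform on 52–104 weeks, walk interpolated as speed, and two-sided Fisher tests at 0.05 on unpaired groups of 20 trial patients and 20, 40 or 60 controls. Rates come from 1,000,000 simulated patients per scenario.

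Closed-form check of the trial rate at noise 0.10 (T25FW) and 0.08 (9-HPT), no true change:

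- walk: P(Z ≥ ln 1.25/(0.10√2) = 1.578) = 5.7%
- 9-HPT: P(Z ≥ ln(4/3)/(0.08√2) = 2.543) = 0.55%
- either: 6.2%

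Results at the 25% cut-off, no true change:

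| Per-visit log-SD, T25FW/9-HPT | Trial rate | Interpolated rate | Rejections favouring NurOwn (20/40/60 controls) |
|---|---|---|---|
| 0.05/0.04 | 0.08% | 0.00% | 0/0/0% |
| 0.075/0.06 | 1.8% | 0.001% | 0.0/0.5/0.5% |
| 0.10/0.08 | 6.2% | 0.05% | 0.7/12.4/12.6% |
| 0.125/0.10 | 12.2% | 0.32% | 8.4/42.2/44.7% |
| 0.15/0.12 | 18.5% | 1.0% | 25.8/65.2/70.9% |

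A 15% cut-off, if it were compared with CLIMB, would be affected earlier: 2.6% against 0.002% at 0.05/0.04, and 11.9% against 0.18% at 0.075/0.06.

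**With true change in the controls** (slopes in log-units per year, 25% cut-off):

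| Noise | Mean slope / SD | True 28-week rate | Interpolated | Uninterpolated 1–2 years |
|---|---|---|---|---|
| 0.10/0.08 | −0.10/0.05 | 2.9% | 0.01% | 1.1% |
| 0.15/0.12 | −0.10/0.05 | 11.9% | 0.3% | 5.9% |
| 0.10/0.08 | 0/0.2 | 13.4% | 5.8% | 38.2% |

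In the first row false rejections are at most 1.9%; in the second they are 7.7/40.8/43.0%. In the first two rows both registry rates are too low. In the third the uninterpolated rate is too high.

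**Where the direction fails.** With slope SD 0.2, no mean change and low noise, true against interpolated rates are 2.3% and 4.0% at zero noise, 2.7% and 4.0% at 0.02/0.016, 3.2% and 4.1% at 0.03/0.024, 4.0% and 4.2% at 0.04/0.032, and 5.0% and 4.4% at 0.05/0.04. The sign changes just below 0.05. Change here is linear in logs, not in ft/sec, so straight-line interpolation is slightly off even without noise.

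**The case against.** The strongest reply is that the plan does not specify this analysis. The appendix describes interpolation without a responder cut-off, section 6.4 says only that a responder comparison may be reported, and the 15%, 20% and 30% cut-offs in section 9.6 are not tied to CLIMB. A reader might infer that the sponsor is committed to testing interpolated responder rates; the documents do not say so. That stands. However, the interpolation itself is a stated rule that yields an individual 28-week value, the primary efficacy endpoint is a cut-off on the same two tests, section 9.1 plans testing against historical data, and nothing excludes the use.

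A second reply is that the available evidence points to a small effect. Protocol section 9.3.4 calls T25FW test-retest reliability high, and both introductions describe gradual worsening. With mean worsening at noise 0.10/0.08, false rejections stay at or below 1.9%. This also stands: the large rejection rates need higher assumed noise. Controls are matched, so a paired test is possible and its error rates would differ.

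A third tempting reading is that interpolation always biases in favour of NurOwn. The low-noise, wide-slope cases show that it does not.

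The allowance for other functions is no answer. It changes the shape of the trend and does not restore visit noise.

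**Conclusion.** The concern holds as a conditional one. Linear interpolation is serviceable for comparing mean change, provided that change is linear on the interpolated scale. It is unsuited to a cut-off applied to individuals. If the ≥25% rule is applied to interpolated values, controls must show an observed improvement of 46% to 93%; that much follows from the documents. Where visit noise is material relative to the spread of true slopes, the control rate is understated and NurOwn is favoured.

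The size rests on assumed noise. With no true change it is negligible at 25% up to a log-SD of about 0.075 and substantial from about 0.125. Below about 0.05 with slope SD 0.2 per year, the direction can reverse slightly. Importance is moderate: the primary endpoint is safety (SAP section 3.2.1) and the responder contrast is optional. It should still be fixed, because the remedy is cheap. Confidence is medium.

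**What to change.** In Appendix I, section 5:

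1. State that linear interpolation of CLIMB data is used only to compare mean change, and that CLIMB T25FW is interpolated in ft/sec, to match sections 3.2.2 and 9.2.
2. State that the ≥25% responder rate will not be tested on interpolated individual values, nor will the other cut-offs if they are compared with CLIMB.
3. If a CLIMB responder rate is shown, present it descriptively. Note that the interpolated rate may be biased and is likely too low when visit noise is material; that the uninterpolated 1–2 year rate is not matched to 28 weeks and may be too high or too low; and that the two do not form a bracket.

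The cost is appendix wording and minor programming, with no new data. The registry contrast becomes less definite.

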9.3.5. Safety analyses

All safety analyses will be based upon the Safety Population.

All AEs will be coded to System Organ Class (SOC) and Preferred Term (PT) using the Medical Dictionary for Regulatory Activities (MedDRA®). The number of treatment-emergent adverse events (TEAEs) and the number of participants with any TEAEs (along with percentages) will be tabulated by SOC and PT.

A TEAE is an AE that occurs for the first time after initiation of treatment or if it had occurred prior to treatment, worsens in severity after initiation of treatment.

Separate summaries will be provided for the following categories of AEs:

- TEAEs
- TEAEs by severity
- Treatment-related TEAEs
- Serious TEAEs

When evaluating changes in safety parameters, Baseline will be defined as the last measurement prior to first transplantation (i.e., prior to initiation of treatment).

Abnormalities in hematology, blood chemistry and ECG assessments will be summarized.

MRI (T1 and T2 weighted images) will be assessed for study safety at baseline and at the end of the study.

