4. STUDY DESIGN

4.1. Summary of Study Design

This is a proof-of-concept Phase 2 open-label study that will be conducted at multiple study sites in 20 participants with progressive MS with EDSS 3.0-6.5 (inclusive) at the Screening Visit. After providing informed consent and signing a written informed consent document all participants will be observed for a total of 9-10 months (38 weeks).

[figure not shown]
During the up to 10-week pretreatment period patients will be screened and eligibility determined. Approximately 1-4 weeks after the screening visit, bone marrow will be harvested and transferred to the cell manufacturing facility for the isolation and cryopreservation of autologous MSCs.

The first transplantation visit (T1) will occur approximately 6 weeks after the bone marrow aspiration visit (6-10 weeks after screening/enrollment). The subsequent transplantation visits (T2 and T3, at visits 4 and 5) will follow interspaced by approximately 8 weeks (± 14 days) each (Figure 1). The subjects will then be followed for 12 additional weeks after the last transplant visit (T3) at two additional visits, approximately 6 weeks apart.

Assessments and procedures that will be performed during the study are provided in Table 2 and Table 3.

Following the third and last treatment, participants will be followed for two additional monthly visits (through week 28) during which the T25FW, 9HPT and other study outcomes (including an MRI assessment at the End of Study visit) will be obtained, along with vital signs, laboratory tests and recording of CMs and AEs [see schedule of assessments (SOA) in Table 2].

Figure 1 Clinical study flowchart

Clinical study flowchart outlining the pre-treatment and the treatment period and the post-transplant follow-up visits. BMA: Bone Marrow Aspiration; T1, T2 and T3, Transplantation 1, 2 and 3. T- Telephone call visit

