8.7. MRI analysis

MRI Data will be analyzed for safety by looking at the following change from baseline to end of study:

- Mean Changes in number of new or enlarging FLAIR lesions on MRI
- Percentage of subjects with $\geq 1, \geq 2, \geq 3$ new or enlarging FLAIR lesions on MRI
- Mean Changes in active FLAIR lesions (new + enlarging) on MRI
- Percentage of subjects with $\geq 1, \geq 2, \geq 3$ active FLAIR lesions (new + enlarging) on MRI
- Mean Change in Total volume of new FLAIR lesions on MRI
- Mean Change in Total volume of FLAIR lesions on MRI

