5.4 MRI

MRI data will also be analyzed for efficacy. Continuous data will be analyzed as changes from baseline and categorical data by counts and percentages.

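### The 28-week registry horizon in SAP Appendix I does not fit MRI, because the trial's two scheduled scans are a nominal 34-38 weeks apart

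*SAP*

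**What the plan says.** **Registry side.** SAP Appendix I, section 5, introduces T25FW and 9-HPT data from matched registry patients and adds: "In addition MRI data was also collected from matched patients in the CLIMB registry data". It then says that the trial will be compared with the registry. Because "data for patients in the CLIMB registry was collected at only two timepoints 1 to 2 years apart", each registry patient's "outcome data will be adjusted by assuming linear change between the two timepoints to estimate the change at 28 weeks". The method is given as "by determining the slope or change in outcome per week using the two timepoints", then adding 28 weeks of that slope to the baseline value. Other functional forms may be explored. No separate rule is given for MRI.

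**Trial side.** SAP section 8.7 states: "MRI Data will be analyzed for safety by looking at the following change from baseline to end of study". The measures are FLAIR lesion counts, the percentages of subjects with at least 1, 2 or 3 lesions, and lesion volumes. Appendix I, section 5.4, adds that "MRI data will also be analyzed for efficacy". Protocol section 9.3.5 says: "MRI (T1 and T2 weighted images) will be assessed for study safety at baseline and at the end of the study".

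**Timing.** In the schedules of assessments (Protocol Table 1, SAP Table 2) the MRI row is ticked at Visit 1 and Visit 7 only. SAP section 4.1 places the first transplantation "6-10 weeks after screening/enrollment". Visit 7 is at Week 28, plus or minus 5 days. Appendix I, section 3.1, takes baseline as the last assessment before first treatment, including unscheduled visits. For MRI, the only scheduled assessment that qualifies is the screening scan.

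**The concern.** The plan uses one time horizon for outcomes whose trial baselines fall on different dates. T25FW and 9-HPT are repeated at Visit 3 before the first injection, so for them the trial change really does cover 28 weeks. The MRI change runs from screening.

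New lesions and lesion volume change build up with time. If they are compared over unequal periods, two groups with the same underlying rate will look different. The trial's stated purpose is to inform a later randomized study, so an MRI contrast that reflects partly the calendar would carry into that design. Part of the trial's MRI interval is also untreated, which any reader of the MRI tables needs to know.

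**Working it through.** **1. Reproduce the plan's own span.** Visit 1 is at Week -10 to -6 and Visit 7 at Week 28.

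- Shortest: 28 + 6 = 34 weeks
- Longest: 28 + 10 = 38 weeks

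This matches the 34-38 weeks of total observation given in the SAP Introduction. Since the only two scans are at the first and last visits, it is also the nominal scan-to-scan interval. With the 5-day window at Visit 7 the interval is 33.3 to 38.7 weeks.

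**2. Compare with the registry target.** At a constant rate, accrual is proportional to time, so the ratio of trial to scaled registry accrual is interval / 28.

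- 34 / 28 = 1.21
- 38 / 28 = 1.36
- With the Visit 7 window: 33.3 / 28 = 1.19 to 38.7 / 28 = 1.38

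**3. Untreated share of the trial interval.** 6 / 34 = 17.6% and 10 / 38 = 26.3%.

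**4. The other reading: registry MRI is not scaled.** Taking 1-2 years as about 52-104 weeks, the trial-to-registry ratio runs from 34 / 104 = 0.33 to 38 / 52 = 0.73. The trial would then appear to accrue fewer lesions at equal rates.

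**5. Illustration in absolute terms.** The documents give no lesion rate, so the rates below are assumptions. Expected lesions = r × weeks / 52.18, and P(at least 1) = 1 − exp(−r × weeks / 52.18).

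| Assumed rate per year | Expected lesions at 28 / 34 / 38 weeks | P(at least 1) at 28 / 34 / 38 weeks |
|---|---|---|
| 0.5 | 0.27 / 0.33 / 0.36 | 23.5% / 27.8% / 30.5% |
| 1 | 0.54 / 0.65 / 0.73 | 41.5% / 47.9% / 51.7% |
| 2 | 1.07 / 1.30 / 1.46 | 65.8% / 72.8% / 76.7% |

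At 0.5 per year the excess is 0.326 − 0.268 = 0.058 to 0.364 − 0.268 = 0.096 lesions per person, or about 1 to 2 lesions over 20 participants. At 2 per year it is 0.230 to 0.383 per person, or about 5 to 8 lesions. The relative excess in P(at least 1) is smaller than 21-36%: at 1 per year it is 47.9 / 41.5 = 1.15 to 51.7 / 41.5 = 1.25.

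**6. Can the linear rule produce the threshold percentages?** No. A registry patient with one new lesion over 52 weeks prorates to 28 / 52 = 0.54 lesions, and over 104 weeks to 28 / 104 = 0.27. Neither value can be classified sensibly as at least 1 or as none.

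**The case against.** Several points can fairly be made against this.

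- **The appendix never says in so many words that MRI is scaled.** This is correct. The formula suits T25FW and 9-HPT, and a count of new lesions has no natural baseline value to which a slope can be added. But the MRI sentence comes directly before the comparison and the scaling rule, and the rule makes no exception. If MRI is in fact left out, step 4 applies. So the direction and the 21-36% depend on the reading, but the inequality of periods does not.
- **A reader might infer that the plan sets up a false safety signal.** The documents do not support that. The MRI safety analysis in SAP section 8.7 is a within-trial change and names no registry comparator. The registry comparison sits under efficacy, and SAP section 5.1 states that there are no formal stopping rules. No safety decision is shown to turn on the scaled comparison.
- **A reader might also infer that the plan attributes pre-treatment lesions to treatment.** It does not say so. It reports change from baseline, and the scan timing is open in the schedule. The lead-in is a limit on interpretation that should be disclosed.
- **The bias is conservative for efficacy, and MRI efficacy is a secondary matter in a 20-person study.** This is true on the natural reading only, and it limits the consequence. It does not make the comparison correct, and the correction is cheap.
- **Actual intervals vary.** Manufacturing slots may move the transplant visits, early-termination scans come sooner, and an unscheduled pre-treatment scan would shorten the interval. All of this stands, and it favours using actual scan dates over any fixed number of weeks.

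**Conclusion.** The point holds in this form: Appendix I gives no time base that aligns registry MRI with trial MRI. On the natural reading, the trial's mean new-lesion accrual and lesion volume change would exceed the scaled registry values by about 21-36% with no true difference, biasing the MRI comparison against the product. On the alternative reading the bias runs the other way.

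The 21-36% rests on the nominal schedule, on equal and constant rates in both groups, and on MRI falling under the scaling rule. It applies to mean counts and volume change, and not to the percentages at each lesion threshold. Allowing other functions changes the shape of the curve but not the 28-week target. The T25FW and 9-HPT comparisons are not affected by this mismatch.

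**What to change.** In Appendix I, section 5, limit the 28-week target to T25FW and 9-HPT and add a rule for MRI:

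- **Counts and volume change:** use a common time base. Either report annualised rates on both sides from actual scan dates, or scale registry values to the trial's actual Visit 1 to Visit 7 scan interval. Use each participant's own interval if matching is one-to-one, and otherwise the trial mean. The documents say only that patients are matched, so the rule should not presume pairs.
- **Percentages with at least 1, 2 or 3 lesions:** do not use linear proration. Use a rate model with log scan interval as an offset, or present each side with its interval stated.
- **MRI tables:** show the length of the untreated lead-in. Putting both sides on one time base does not remove that untreated time from the trial's change.

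The cost is a few sentences and slightly more analysis work. It needs scan dates but no new scan or visit, and the registry slope calculation already requires the registry intervals. The remaining assumption is a constant rate, which the plan's linear rule already makes.
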